4.1.2 Exclusion Criteria

- 1. Patient cannot swallow oral medication.
- 2. Patient is on gliptins.
- 3. Patient has active central nervous system (CNS) metastases not controlled by prior surgery or radiotherapy (patient must be off steroids). Patients with signs or symptoms suggestive of brain metastasis are not eligible unless brain metastases are ruled out by brain MRI/CT.
- 4. Patient has received external-beam radiation or another systemic anticancer therapy within 14 days or 5 half-lives, whichever is shorter, prior to study treatment.
- 5. Patient has received treatment with an investigational systemic anticancer agent within 14 days prior to study drug administration.
- 6. Patient has an additional active malignancy that may confound the assessment of the study endpoints. Patients with the following concomitant neoplastic diagnoses are eligible: non-melanoma skin cancer and carcinoma *in situ* (including transitional cell carcinoma, anal carcinoma, and melanoma *in situ*). Patients with simultaneous cancers, which are not active and do not require treatment may be eligible contingent on discussion with the PI and supporter.
- 7. Patient has clinically significant cardiovascular disease (e.g., uncontrolled or any New York Heart Association Class 3 or 4 congestive heart failure, uncontrolled angina, history of myocardial infarction, unstable angina or stroke within 6 months prior to study entry, uncontrolled hypertension or clinically significant arrhythmias not controlled by medication).
- 8. Patients with a history of clinically significant hypotension within past 3 months.
- 9. Patients, who are unable to maintain adequate hydration of ≥ 2 liters per day.
- 10. Patient has a diagnosis of immunodeficiency or is receiving systemic steroid therapy at a prednisone equivalent dose of >10 mg daily for at least 1 week or other form of immunosuppressive therapy within 7 days prior to Cycle 1 Day 1 (C1D1).
- 11. Patient has uncontrolled intercurrent illness including, but not limited to, uncontrolled infection, disseminated intravascular coagulation, or psychiatric illness/social situations that would limit compliance with study requirements.
- 12. Patient has known positive status for human immunodeficiency virus active or chronic Hepatitis B or Hepatitis C. Patients with history of hepatitis B or C and undetectable viral load are eligible. Screening is not required.
- 13. Has a clinically significant upper gastrointestinal obstruction, abnormal physiological function or malabsorption syndrome that may affect the absorption of the study medication.
- 14. Patient has any medical condition which, in the opinion of the investigator, places the patient at an unacceptably high risk for toxicity.
- 15. Patient is pregnant or breast-feeding

5 STUDY METHODOLOGY

5.1. Concomitant Medications

5.1.1 Permitted Medications/Therapies

The use of growth factors (e.g., granulocyte-colony stimulating factor [G-CSF]) is allowed as clinically indicated for the treatment of Grade \geq 3 cytopenias.

Suggested supportive care measures for the management of AEs with potential immunologic etiology are outlined below. Where appropriate, these guidelines include the use of oral or IV treatment with corticosteroids as well as additional anti-inflammatory agents if symptoms do not improve with administration of corticosteroids. Note that several courses of steroid tapering may be necessary as symptoms may worsen when the steroid dose is decreased. For each AE, attempts should be made to rule out other causes such as metastatic disease or bacterial or viral infection, which might require additional supportive care.

5.1.2 **Prohibited Medications/Therapies**

Enrolled patients may not receive investigational or approved anticancer agents including cytotoxic chemotherapy agents, anticancer tyrosine kinase inhibitors, or therapeutic monoclonal antibodies.

Concurrent radiation is not permitted with the exception of palliative radiation of limited number of isolated solitary lesions.

Preclinical studies have demonstrated a low potential for BXCL701 to inhibit the following major human liver CYP isoenzymes: CYP1A2, CYP2C8, CYP2C9, CYP2C19, CYP2D6, and CYP3A4. Further, relevant concentrations of BXCL701 did not induce CYP3A4 or CYP1A2. Therefore, there are no prohibited medications based on CYP isoenzymes.

5.2. Efficacy Assessments

Efficacy will be assessed during treatment using the RECIST 1.1 and iRECIST every 9 weeks (every 3 cycles). Intervals can be shortened to 6 weeks (every 2 cycles) if clinically necessary per treating physician. Details on RECIST and iRECIST are described in Appendix B and C. [19, 20] Tumor measurements will be in QIAC.

5.3. Safety Assessments

5.3.1. Non-Serious Adverse Events

An Adverse Event is defined as any untoward medical occurrence in a patient regardless of its causal relationship to study treatment. An AE can be any unfavorable and unintended sign (including any clinically significant abnormal laboratory test result), symptom, or disease temporally associated with the use of the study treatment, whether or not it is considered to be study drug(s) related. Included in this definition are any newly occurring events and any previous condition that has increased in severity or frequency since the administration of study therapy. Investigators should assess for AEs at each visit. All AEs, including observed or volunteered problems, complaints, or symptoms, are to be recorded on the eCRF. Each AE is to be evaluated for duration, intensity, and causal relationship with the study treatment or other factors. MOCLIA will be used for eCRF in this study. Department (Investigational Cancer Therapeutics) database team will create the CRF based on protocol requirement and IND monitor will review and approve it once ready.

The investigator is responsible for monitoring the safety of patients who have entered the study. All AEs occurring during the treatment period and/or occurring within 30 days of the last dose of BXCL701 and or pembrolizumab (investigational products, IPs) will be followed to the end of the study or until resolution. AEs will be graded according to the revised NCI CTCAE, Version 5.0, (see http://ctep.cancer.gov/reporting/ctc.html). AEs occurring 30 days after the last dose of IPs do not need to be reported unless the investigator considers the event to be related to IPs.

Clinical laboratory data are to be collected in this study, and toxicity trends will be analyzed utilizing objective toxicity criteria. Abnormal laboratory findings considered clinically significant by the investigator and outside the expected deviation for a patient with IPs should be reported as AEs. Wherever possible, a specific disease or syndrome rather than individual associated signs and symptoms should be identified by the investigator and recorded on the eCRF. Clinical syndromes associated with laboratory abnormalities are to be recorded as such (e.g., diabetes mellitus instead of hyperglycemia). However, if an observed or reported sign or symptom is not considered a component of a specific disease or syndrome by the investigator, it should be recorded as a separate AE on the eCRF.

PD should not be reported as an AE (see Section 5.7) unless the patient dies solely due to PD within 30 days of the last dose of IPs.

The relationship of each AE to each study drug (BXCL701 and/or pembrolizumab) will be evaluated by the investigator using the following definitions:

- Not related: The AE is clearly not related to the study drug(s). The AE can be explained to be likely related to other factors such as concomitant medications or the patient's clinical state.
- Possibly related: The AE may be related to the investigational agent(s). A plausible temporal sequence exists between the time of administration of the investigational product and the development of the AE, and it follows a known response pattern to the investigational product. The reaction may have been produced by the patient's clinical state or other concomitant therapies or interventions.
- Related: The AE is clearly related to the investigational agent(s). A plausible temporal sequence exists between the time of administration of the investigational product and the development of the AE, and it follows a known response pattern to the investigational product. The occurrence of this AE can be confirmed with a positive re-challenge test or supporting laboratory data.

The causality criteria of related and possibly related will be considered "related" to the study drug(s) for regulatory reporting requirements.

The investigator (or physician designee) is responsible for verifying and providing source documentation for all adverse events and assigning the attribution for all adverse events for subjects enrolled.

Attribution	Grade 1	Grade 2	Grade 3	Grade 4	Grade 5
Unrelated	Phase I	Phase I	Phase I	Phase I	Phase I
			Phase II	Phase II	Phase II
				Phase III	Phase III
Unlikely	Phase I	Phase I	Phase I	Phase I	Phase I
-			Phase II	Phase II	Phase II
				Phase III	Phase III
Possible	Phase I	Phase I	Phase I	Phase I	Phase I
	Phase II	Phase II	Phase II	Phase II	Phase II
		Phase III	Phase III	Phase III	Phase III
Probable	Phase I	Phase I	Phase I	Phase I	Phase I
	Phase II	Phase II	Phase II	Phase II	Phase II
		Phase III	Phase III	Phase III	Phase III
Definitive	Phase I	Phase I	Phase I	Phase I	Phase I
	Phase II	Phase II	Phase II	Phase II	Phase II
		Phase III	Phase III	Phase III	Phase III
Probable	Phase II Phase I Phase II Phase I	Phase II Phase III Phase I Phase II Phase III Phase I Phase II	Phase II Phase III Phase I Phase II Phase III Phase I Phase II	Phase II Phase III Phase I Phase II Phase III Phase I Phase II	Phase II Phase III Phase I Phase II Phase III Phase I Phase II

Recommended Adverse Event Recording Guidelines

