5.3.2. Reporting Serious Adverse Events

An adverse event or suspected adverse reaction is considered "serious" if, in the view of the investigator, it results in any of the following outcomes:

- Death
- A life-threatening adverse drug experience any adverse experience that places the patient, in the view of the initial reporter, at immediate risk of death from the adverse experience as it occurred. It does not include an adverse experience that, had it occurred in a more severe form, might have caused death.
- Inpatient hospitalization or prolongation of existing hospitalization
- A persistent or significant incapacity or substantial disruption of the ability to conduct normal life functions.
- A congenital anomaly/birth defect.

Important medical events that may not result in death, be life-threatening, or require hospitalization may be considered a serious adverse drug experience when, based upon appropriate medical judgment, they may jeopardize the patient or subject and may require medical or surgical intervention to prevent one of the outcomes listed in this definition. Examples of such medical events include allergic bronchospasm requiring intensive treatment in an emergency room or at home, blood dyscrasias or convulsions that do not result in inpatient hospitalization, or the development of drug dependency or drug abuse (21 CFR 312.32).

- Important medical events as defined above, may also be considered serious adverse events. Any important medical event can and should be reported as an SAE if deemed appropriate by the Principal Investigator or the IND supporter, IND Office.
- All events occurring during the conduct of a protocol and meeting the definition of a SAE must be reported to the IRB in accordance with the timeframes and procedures outlined in "The University of Texas M. D. Anderson Cancer Center Institutional Review Board Policy for Investigators on Reporting Serious Unanticipated Adverse Events for Drugs and Devices". Unless stated otherwise in the protocol, all SAEs, expected or unexpected, must be reported to the IND Office, regardless of attribution (within 5 working days of knowledge of the event).
- All life-threatening or fatal events, that are unexpected, and related to the study drug, must have a written report submitted within 24 hours (next working day) of knowledge of the event to the Safety Project Manager in the IND Office.

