- Unless otherwise noted, the electronic SAE application (eSAE) will be utilized for safety reporting to the IND Office and MDACC IRB.
- Serious adverse events will be captured from the time of the first protocol-specific intervention, until 30 days after the last dose of drug or earlier if the participant withdraws consent or starts a new anti-cancer therapy. Serious adverse events must be followed until clinical recovery is complete and laboratory tests have returned to baseline, progression of the event has stabilized, or there has been acceptable resolution of the event.
- Additionally, any serious adverse events that occur after the 30 day time period that are related to the study treatment must be reported to the IND Office. This may include the development of a secondary malignancy.

Reporting to FDA:

• Serious adverse events will be forwarded to FDA by the IND supporter (Safety Project Manager IND Office) according to 21 CFR 312.32.

It is the responsibility of the PI and the research team to ensure serious adverse events are reported according to the Code of Federal Regulations, Good Clinical Practices, the protocol guidelines, the supporter's guidelines, and Institutional Review Board policy.

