6.2 Dose Adjustments of BXCL701 Secondary to Toxicity

BXCL701 dose modifications (other than recommended in the protocol) within a treatment cycle are discouraged in Cycle 1 unless required by AE and/or DLT. In Cycle \geq 2, dose modifications within a treatment cycle will be at the discretion of the investigator. Doses held because of AEs should not be made up on subsequent days within or following a cycle. A dose that is missed for reasons other than an AE (i.e., the patient forgets to take a dose) may be administered on days subsequent to scheduled doses; any such adjustments should be discussed with the Investigator. Under no circumstances should missed doses be made-up on a day when the patient is already taking a planned dose (i.e., no "doubling-up" to account for missed doses).

Recommendations for BXCL701 dose modifications are:

- Do not administer BXC701 if systolic blood pressure obtained before dosing is less than 100 mmHg
- Grade 2 or higher AEs of edema/peripheral swelling, hypotension, dizziness, and hypovolemia:

- \circ For Grade 3 AEs, hold/interrupt BXCL701until resolution of these AEs to \leq Grade 1 or baseline. Thereafter, restart BXCL701 at a dose reduced by 0.2 mg (reduction of 0.1 mg twice day to 0.2 mg twice a day; 1 dose level reduction).
- For Grade 2 AEs, hold/interrupt BXCL701 until resolution of these AEs to \leq Grade 1 or baseline. Thereafter, resume at the full dose or at a dose reduced by 0.2 mg (reduction of 0.1 mg twice day to 0.2 mg twice a day; 1 dose level reduction) at the discretion of the investigator.
- For any Grade 3 or higher edema or Grade 2 edema that has not improved within 7 days, restart BXCL701 at a dose reduced by 0.2 mg (reduction of 0.1 mg twice day to 0.2 mg twice a day; 1 dose level reduction) after resolution of the edema to ≤ Grade 1 or baseline.
- For other Grade 2 or higher AEs deemed related to BXCL701:
 - Hold BXCL701 until resolution of these AEs to \leq Grade 1 or baseline.
 - For Grade 2 AEs, restart BXCL701 at the full dose or at a dose reduced by 0.2 mg (reduction of 0.1 mg twice day to 0.2 mg twice a day; 1 dose level reduction) at the discretion of the Investigator.
 - For Grade 3 AEs, restart BXCL701 at a dose reduced by 0.2 mg (reduction of 0.1 mg twice day to 0.2 mg twice a day; 1 dose level reduction).
- Once BXCL701 dose has been de-escalated, it may **not be** re-escalated.

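### Both positive causality categories in Section 5.3.1 require a known response pattern, so a new type of toxicity fits no category and can miss the 24-hour report

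*Combined protocol and SAP*

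**What the plan says.** Section 3 sends attribution to the criteria in Section 5.3.1, which has the investigator rate each AE against each drug in one of three categories:

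- *Not related*: clearly unrelated, and explicable by other factors.
- *Possibly related*: the drug may be a cause, the timing is plausible, "and it follows a known response pattern to the investigational product". Another explanation may also exist.
- *Related*: clearly drug-related, with the same timing and known-pattern conditions word for word, plus possible confirmation by re-challenge or laboratory data.

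Only the last two count as related for regulatory reporting. The recording table that closes the section uses five other terms: Unrelated, Unlikely, Possible, Probable and Definitive.

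Relatedness is then used elsewhere:

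- Section 5.3.2, fast report: "All life-threatening or fatal events, that are unexpected, and related to the study drug, must have a written report submitted within 24 hours". The text glosses this limit as the next working day.
- Section 5.3.2, late SAEs: "any serious adverse events that occur after the 30 day time period that are related to the study treatment must be reported". Section 5.3.1 makes late AE reporting depend on relatedness in a similar way.
- Section 6.2: "For other Grade 2 or higher AEs deemed related to BXCL701" introduces one set of BXCL701 rules. The 6-week non-recovery rule and the SAE interruption rule also refer to relatedness.
- Section 7.1: AE tables are subdivided by relationship to study drug.

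**The concern.** An event of a type not seen before with either drug has, on the ordinary meaning of the words, no known response pattern to follow. It is therefore hard to place in either positive category, however suggestive the timing. The fast report is meant for events that are both unexpected and related. A new type is the plainest way for an event to be unexpected, and it is also the case in which the definitions make *related* hard to assign.

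This matters more than usual here. The rationale in the Summary and Section 1 is synergy between two immune-active agents. Section 3.1 expects combined toxicity no greater than the sum of the separate toxicities, and attribution is made drug by drug. A toxicity that arises only from the interaction might match neither drug's known pattern. Section 3.1 also shows that safety knowledge is still developing, since emerging data on early hypotension led to a changed Cycle 1 schedule.

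At stake are the speed of reporting for a serious new toxicity, consistent application of the relatedness-based rules, and the treatment-related columns of the AE tables. The response endpoints are not affected.

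**Working it through.** The plan gives no figure to reproduce, and no arithmetic beyond one subtraction applies. The check is logical.

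**Conditions.** Let T = plausible timing, K = follows a known response pattern, N = clearly not related. Section 5.3.1 joins T and K with *and* in both positive categories, so:

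- *Possibly related* requires T and K.
- *Related* requires T and K, and more.
- *Not related* requires N.

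**Three test events**, reading a known pattern as an event type already associated with the drug:

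| Event | T | K | N | Category available |
|---|---|---|---|---|
| Known type, usual severity | yes | yes | no | a positive category |
| Known type, unexpected severity | yes | yes | no | a positive category |
| New type, no other clear cause | yes | no | no | none |

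The third event is unclassifiable. The recording table does not settle it, because its five terms are neither defined nor mapped to the three categories.

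**Rules applied to the third event:**

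| Rule | Uses attribution? | Result |
|---|---|---|
| Fast report, 5.3.2 | yes | not triggered as written |
| General SAE report, 5.3.2 | no | applies within the capture window, 5 working days |
| Late SAE report, 5.3.2 | yes | ambiguous |
| Late AE report, 5.3.1 | yes, investigator's view | ambiguous |
| Late AE report, 5.4 | separate test: whether the drug is thought to have contributed | can apply |
| Other Grade 2 or higher AEs, 6-week non-recovery and SAE interruption, 6.2 | yes, as deemed or thought | ambiguous |
| Edema, hypotension, dizziness and hypovolemia, 6.2 | no | these are known types, so the gap does not arise |
| Any life-threatening AE, 6.2 and 8.5.1 | no | applies |
| Cycle 1 DLT, Section 3 | no, unless an extraneous cause is incontrovertible | applies |
| AE tables by relationship, 7.1 | yes | omitted or placed inconsistently |

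**Size of the reporting delay.** Taking the 24-hour limit as 1 working day, as the text glosses it, and the general limit as 5 working days, the latest permitted report moves by 5 − 1 = 4 working days.

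**The case against.** The strongest reply is that investigators will use judgement. *Possibly related* opens by saying only that the drug may be a cause. The phrase on known patterns is undefined and could be read as consistent with known pharmacology, which for these drugs is broad: cytokine activation for BXCL701, and immune-mediated events in many body systems for pembrolizumab. Several downstream rules turn on what is deemed, thought or considered related, and much of the safety system does not use attribution at all.

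Much of this stands, and it rules out stronger readings that a reader might infer:

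- *No new toxicity could ever be rated related.* This depends on one reading of an undefined phrase. A broader reading admits some new events.
- *The fast report can never be triggered.* The documents do not define unexpected, so a known event type of unexpected severity can meet both conditions.
- *Late non-serious toxicity would go unreported.* Section 5.4 has its own contribution test, with no known-pattern condition.
- *The BXCL701 dose rules fail for the events they exist to catch.* Those rules mainly serve known toxicities, for which they work. Life-threatening events are covered without attribution, and from Cycle 2 dose modification within a cycle is at the investigator's discretion.
- *New events would be recorded as unrelated, biasing treatment-related rates downward.* The text does not send them there, because *Not related* has its own strict condition. The supported result is an event without a category. Section 7.1 also tabulates AEs overall, so the event stays visible.

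The appeal to judgement does not remove the gap. The definition adds a condition after its permissive opening and gives no leave to waive it. Two careful readers could therefore code the same event differently.

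**Conclusion.** The point holds in limited form. As written, the three categories do not cover a toxicity of a new type with plausible timing and no other clear cause. If that event is fatal or life-threatening, it does not meet the trigger for the 24-hour report and moves to the 5-working-day route, up to 4 working days later. Any SAE within the capture window still reaches the IND Office. For less severe events, the effect is ambiguity in the relatedness-based rules of Sections 5.3.1, 5.3.2 and 6.2, and inconsistent placement in the Section 7.1 tables.

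This rests on two assumptions: that a known response pattern means an event type already associated with the drug, and that the investigator applies the definition literally. The documents give no basis for estimating how often such an event would occur, or how far treatment-related rates would change. The defect is a correctable fault in one definition. It leaves the response analysis and the Cycle 1 DLT count untouched.

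**What to change.** Four wording changes:

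1. In Section 5.3.1, remove the known response pattern as a condition of *Possibly related*. The category would require plausible timing and a reasonable possibility that the drug played a causal role.
2. In *Related*, list a known response pattern as one form of supporting evidence, not as a requirement.
3. Align the three defined categories with the five terms of the recording table, or state how they map, and carry the same list into the eCRF completion guide.
4. Reconcile the late-reporting wording of Section 5.3.1 with that of Section 5.4, so that one test applies after 30 days.

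A blanket default of every AE not clearly unrelated to *Possibly related* is not needed. It would bring ambiguous events under the relatedness-based holds, reductions and discontinuation in Section 6.2.

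The drafting cost is small. Some more AEs will be rated possibly related, so the treatment-related rate may rise slightly and the existing relatedness-based rules in Section 6.2 may apply a little more often. The clinical team should be aware of that effect. No dose or management rule is changed.
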